5.7.6 Patient-completed questionnaires

The Skindex-29 is a questionnaire that results in three scales: emotions, symptoms, and functioning [Chren 1996, Chren 1997a, Chren 1997b, Chren 2001]. Appendix A shows the items in the Skindex-29 questionnaire and Appendix B describes the scoring of individual items to the 3 scales. To compute the scale, each item is first transformed to a linear 0–100 scale where responses of “Never”, “Rarely”, “Sometimes”, “Often”, and “All the time” are converted to values of 0, 25, 50, 75, and 100, respectively. Next, the mean of the non-missing items for each scale is computed to derive a scale score. Although missing data for individual items is allowed, no scale score will be computed if more than quarter of the items in the scale are missing.

The VAS for pruritus is a single value [Reich 2012] and is shown in Appendix C.

The MF/SS-CTCL questionnaire contains 12 questions [PatientsLikeMe 2016] and is shown in Appendix D.

At each study visit (1st, 2nd, etc.), the VAS for pruritus, the three scales of the Skindex-29 and the MF/SS-CTCL will be computed for patients who are and are not responders,

based on clinician assessment, at the time of that visit. These descriptive cross-sectional comparisons are intended to assess burden of disease in a Valchlor-treated cohort over time. The data related to all three questionnaires (VAS, Skindex-29, MF/SS-CTCL) will be collected on the QOL questionnaires.

5.8 Quality control

The use of the EDC system will allow for on-line data quality checks upon data entry. The EDC system will have pre-programmed automatic edit checks for data inconsistencies at the time of data entry, and resulting queries will be addressed by the site.

Site visits may be conducted by Actelion or by an authorized Actelion representative to inspect study data, patient medical records, and eCRFs.

No source data verification is mandated. However, the data will be reviewed on an ongoing basis for implausible data points, missing data points, assessments not conducted, and/or incomplete information. This review may result in queries to the sites. Centralized remote monitoring of patient data will be performed via the EDC tool. This approach will allow proactive monitoring and querying of data on an ongoing and regular basis with concentrated efforts on key data points (e.g., hospitalization, death, Valchlor interruption and discontinuation, AEs and SAEs, and secondary exposures) to encourage low rates of missing information. Communication with investigators and study coordinators will emphasize the importance of data entry completion. Analytical methods described in Section 5.7 will be applied to assess the extent of the missing data and the impact on inferential estimates.

5.9 Discussion of the study methods (including limitations)

This study is an observational, prospective study examining MF-CTCL patients being treated with Valchlor in a real-world clinical setting. Valchlor treatment will be based on prescriber decision and will not be influenced by participation in this study. The patients will be followed by their physician according to routine clinical practice. The study protocol does not mandate any treatment, procedures or visits. Patient-completed questionnaires, however, are a study requirement and will be administered at all study visits for patients who can read and understand English, and are physically and mentally able to complete the questionnaires based on the investigator's assessment.

Any interpretation of observational study results should consider limitations to observational real-world study designs, including potential sources of selection or information biases, and confounding factors.

To minimize selection bias, participating centers will offer enrollment in the study to all consecutive MF-CTCL patients currently treated with Valchlor [see Section 5.2.1 for inclusion criteria], regardless of other MF-CTCL specific therapy received before or at

the time of enrollment, or during the study. This study collects data on all users of Valchlor. At enrollment, a review of existing medical records will be performed to collect information as described per [Table 1](#) (enrollment visit). Thereafter, all data will be collected during the observation period.

Patients who are enrolled under the original protocol prior to protocol Amendment 1 and are still ongoing in the study will be re-consented under Amendment 1 and will continue to follow the schedule of Table 1 eCRF Data Collection specified in this protocol up to end of study (Month 24). Patients who enrolled and have completed 1 year of the study under the original protocol will not be offered to continue in the study and thus not re-consented under Amendment 1.

To minimize the number of patients lost to follow-up, there will be regular contact with patients by the site, including 3 attempts to contact a patient before she/he is considered lost to follow-up.

6 PROTECTION OF HUMAN SUBJECTS AND ETHICAL APPROVAL

6.1 Institutional Review Board/Independent Ethics Committee approval

Depending on local regulations and the physician's institutional policies, and in compliance with local law, the physician may have to submit the study protocol, the form for the Patient Informed Consent, and other relevant information to an Institutional Review Board (IRB) / Independent Ethics Committee (IEC), local health authorities, data protection agency or others. Approval from the IRB/IEC must be obtained before going through a consent procedure with the patient and before entering data into the database. IRB/IEC information/approval must be documented in a letter to the physician, clearly identifying the study, the documents reviewed, and the date of approval.

6.2 Patient informed consent

The participating physician commits to obtaining approval for the Patient Informed Consent Form from his/her respective Research Ethics Board, if required by applicable site policies, national privacy regulations and other state and local laws relating to medical information, prior to commencement of the project. Moreover, if required, the participating physician will obtain a signed Patient Informed Consent Form from each patient (or legal guardian) whose data will be included in the project.

6.3 Patient confidentiality

By signing the protocol, the participating physician commits to complying with all related applicable local laws and regulations, including but not limited to the regulations in 45 CFR parts 160 and 164 (protected health information), such regulations also known as the "HIPAA Privacy Regulations".

7 MANAGEMENT AND REPORTING OF ADVERSE EVENTS

With reference to collecting, processing and expediting of AE reports, Actelion as the sponsor of this prospective non-interventional study complies with international and national pharmacovigilance regulations.

7.1 Definitions

7.1.1 Adverse event or adverse experience

Any untoward medical occurrence in a patient administered a pharmaceutical product and which does not necessarily have a causal relationship with this treatment. An AE can therefore be any unfavorable and unintended sign (including an abnormal laboratory finding), symptom, or disease temporally associated with the use of a medicinal product, whether or not related to the medicinal product.

AEs include:

Recurrence or worsening of a pre-existing disease.

Increase in frequency or intensity of symptoms of a pre-existing disease or medical condition.

Continuous persistent disease or symptoms present at initiation of treatment or enrollment, which occurs first, that worsen following the start of the study.

Lack of efficacy in the acute treatment of a life-threatening disease. Abnormal assessments, e.g., ECG, vital signs, or physical examination findings, if they represent a clinically significant finding that was not present at initiation of treatment or enrollment, which occurs first, or worsened during the course of the study or led to dose reduction, interruption or permanent discontinuation of Valchlor.

Laboratory test abnormalities if they represent a clinically significant finding, symptomatic or not, which were not present at initiation of treatment or enrollment, which occurs first, or worsened during the course of the study or led to dose reduction, interruption or permanent discontinuation of Valchlor.

In addition to AEs, exposure during pregnancy or lactation, product complaints, medication errors, overdose, misuse, abuse, occupational exposure and transmission of an infectious agent via Valchlor and the identification of a potential counterfeit medicinal product needs to be reported.

Reports of off-label use without an associated AE collected within non-interventional studies shall be included in final study reports.

Reports of inadvertent secondary exposure to the skin, mucous membranes, and eyes of individuals other than the patient being treated (e.g., patient's caregiver or family member).

AEs do not include:

Medical procedures such as surgery, endoscopy, tooth extraction. However, the event that led to the intervention is considered an AE.

Situations in which no undesirable change occurred, such as hospitalization for cosmetic surgery or for social reasons.

7.1.2 Serious adverse events

An SAE is defined by the International Conference on Harmonisation guidelines as any AE fulfilling at least one of the following criteria:

Fatal.

Life-threatening: refers to an event in which the subject was at risk of death at the time of the event. It does not refer to an event that hypothetically might have caused death had it been more severe.

Requiring inpatient hospitalization, or prolongation of existing hospitalization.

Resulting in persistent or significant disability or incapacity.

Congenital anomaly or birth defect.

Medically significant: refers to important medical events that may not immediately result in death, be life-threatening, or require hospitalization but may be considered to be SAEs when, based upon appropriate medical judgment, they may jeopardize the subject, and may require medical or surgical intervention to prevent one of the outcomes listed in the definitions above.

The following reasons for **hospitalizations** are exempted from being reported:

Hospitalizations for cosmetic elective surgery, or social and/or convenience reasons.

Hospitalization for pre-planned (prior to enrollment) standard monitoring of a pre-existing disease (present at enrollment) or medical condition that did not worsen, e.g., hospitalization for coronary angiography in a patient with stable angina pectoris.

Hospitalizations for elective treatment of a pre-existing disease (present at enrollment) or medical condition that did not worsen, e.g., elective hip replacement for arthritis.

New AEs and SAEs that occur > 30 days after the discontinuation of Valchlor unless there is a reasonable possibility of causal relationship to Valchlor.

However, complications that occur during such hospitalizations are AEs or SAEs (for example, if a complication prolongs hospitalization) and must be reported as described below.

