5.2.1 Inclusion criteria

- All adult patients (≥ 18 years of age) diagnosed with MF-CTCL and being treated with Valchlor. This includes patients newly initiating Valchlor OR patients continuing treatment with Valchlor:
 - Patients newly initiating Valchlor are patients who have their first office visit after having initiated Valchlor.
 - Patients continuing treatment with Valchlor includes patients who are actively taking Valchlor on the day of enrollment.
- Signed patient informed consent.

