## ANALYSIS POPULATIONS

This study will enroll approximately 300 MF-CTCL patients who are being treated (newly initiated or continuing treatment) with Valchlor from up to 50 participating university-affiliated hospitals, community hospitals, or community clinics in the United States.

Patients considered 'being treated with Valchlor' are composed of two distinct groups:

- 1) Patients who are newly initiating Valchlor treatment (i.e. patients who have initiated Valchlor within 30 days or fewer prior to enrollment) and,
- 2) Patients who are continuing treatment with Valchlor (i.e. patients who have been on Valchlor for more than 30 days prior to enrollment).

Patients in either group must be treated with Valchlor at enrollment to be eligible for the study.

All consecutive MF-CTCL patients who are receiving Valchlor at participating US centers are eligible for enrollment in the study, regardless of other MF-CTCL therapies received before or at the time of enrollment.

The primary efficacy endpoint will be the proportion of subjects who are responders to treatment at the 12-month timepoint using a  $\geq 50\%$  reduction from baseline in BSA as the definition of a responder in the group of patients who used mechlorethamine plus corticosteroids and possibly another treatment. Since PROVe did not require a specific visit schedule, the primary 12-month analysis will include patients with a post-baseline % BSA score that falls within a window of  $365 \pm 90$  days. Please note that in this observational trial, patients continued on study even if they permanently discontinued mechlorethamine gel for any reason and switched to new therapy. Given this, such patients (15-20%) will be excluded from the analysis at 12 months. A sensitivity analysis will be conducted for the primary analysis using the full dataset. We will compare this to the subset of patients who discontinued mechlorethamine gel (Table 21a).

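### The hospitalization exemptions in protocol Section 7.1.2 date pre-existing disease from enrollment, after Valchlor has started, so a narrow class of admissions for conditions arising on the drug need not be reported as SAEs

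*Protocol*

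**What the plan says.** Section 7.1.2 of the protocol lists reasons for hospitalization that "are exempted from being reported". Two of them depend on a disease being pre-existing, and both date that from enrollment:

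- elective treatment: "Hospitalizations for elective treatment of a pre-existing disease (present at enrollment) or medical condition that did not worsen";
- monitoring: "Hospitalization for pre-planned (prior to enrollment) standard monitoring of a pre-existing disease (present at enrollment) or medical condition that did not worsen".

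Complications during an exempt admission stay reportable.

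Section 7.1.1, which defines an adverse event, uses a different date. Among the events that count it lists "Continuous persistent disease or symptoms present at initiation of treatment or enrollment, which occurs first, that worsen following the start of the study". The same earlier-of-two-dates rule appears there for abnormal assessments and for laboratory findings. Section 7.2 requires SAEs to be collected and reported from the start of Valchlor until 30 days after it is stopped.

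On eligibility, Section 5.2.1 of the protocol says "Patients newly initiating Valchlor are patients who have their first office visit after having initiated Valchlor" and "Patients continuing treatment with Valchlor includes patients who are actively taking Valchlor on the day of enrollment". The SAP (Analysis Populations) says of both groups: "Patients in either group must be treated with Valchlor at enrollment to be eligible for the study".

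**The concern.** An exemption for pre-existing disease is meant to keep admissions that have nothing to do with the drug out of the SAE count. That works when the baseline date precedes treatment. Here enrollment follows the start of treatment in every patient, so the exemption also covers conditions that first appeared on Valchlor.

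Describing the incidence of AEs and SAEs is a stated objective (protocol Section 4), and real-world safety is part of the rationale (Section 3). A rule that can remove only on-drug events works against that objective. It also leaves sites without a single rule: one that follows Sections 7.1.1 and 7.2 would report an admission that another, following Section 7.1.2, would not.

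**Working it through.** The plan gives no figure to reproduce, and the point does not depend on one. It rests on comparing dates.

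**1. Which date comes first.** New users enroll at an office visit after starting Valchlor; continuing users are on it on the day of enrollment (protocol Section 5.2.1; SAP, Analysis Populations). Treatment start therefore precedes enrollment, and the earlier-of-two-dates rule in Section 7.1.1 resolves to treatment start.

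**2. The anchors side by side.**

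| Rule | Reference date | What that means here |
|---|---|---|
| 7.1.1, presence of a condition | Earlier of treatment start and enrollment | Treatment start |
| 7.1.1, worsening of persistent disease | Start of the study | After enrollment |
| 7.2, SAE reporting window | Valchlor initiation | Treatment start |
| 7.1.2, presence, both exemptions | Enrollment | Later than treatment start |

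Section 7.1.2 is the outlier on presence.

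**3. The interval affected.** It runs from first Valchlor use to enrollment. The SAP puts it at 30 days or fewer for new users, and defines continuing users as "patients who have been on Valchlor for more than 30 days prior to enrollment". It adds that the two groups differ by about 3 months on average. The protocol sets no day limit for new users.

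**4. What is lost.** Take a condition with onset in that interval that is still present at enrollment. After enrollment the patient is admitted for elective treatment, or for monitoring planned before enrollment, and the condition has not worsened. Inpatient hospitalization is a seriousness criterion in Section 7.1.2, but the exemption removes this admission from reporting. If no other criterion applies, the event is not reported as an SAE.

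**5. Whether other collection closes the gap.**

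- Protocol Table 1 records AEs and SAEs ongoing at enrollment. That keeps the condition, but not a later admission as a criterion for seriousness.
- Section 7.1.1 keeps the event behind a procedure as an AE, which does not make it an SAE.
- The complications clause covers only what happens during the admission.
- Protocol Table 1 limits healthcare utilization to MF-CTCL-related admissions. The SAP shell for Table 16 has a row for all hospitalizations, but the protocol does not clearly collect data for it, and a utilization count is not an SAE report.

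**6. Scale.** The documents give no count of such conditions or admissions, so no frequency can be calculated. The effect of one missed patient can be shown under two assumptions: that the patient has no other SAE, and that the denominator is as stated. With the N = 289 of SAP Table 28 it is 1/289 = 0.35 percentage points. The Table 19 shell reports by combination group, and those group sizes are not given. If the Table 28 counts during treatment stand in for them, one patient is 1/88 = 1.1 points (topical corticosteroids), 1/36 = 2.8 points (systemic retinoids) or 1/33 = 3.0 points (phototherapy). These are per-patient illustrations, not estimates of bias.

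**The case against.** The strongest reply is that the case needs many things at once: onset between Valchlor start and enrollment, persistence to enrollment, a later admission that is elective or pre-planned, no worsening, no complication, and no other ground for seriousness. The protocol's own examples, stable angina and hip arthritis, are ordinary background disease. This stands, and it is why the point is narrow.

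A reader might infer that the seriousness of these conditions is never recorded, or that they appear at most as an ongoing AE. The documents do not support either. Hospitalization is one of six seriousness criteria, and the others, including medical significance, still apply. SAEs ongoing at enrollment are recorded. Malignancies and non-melanoma skin cancers have their own enrollment rows in protocol Table 1, and changes in medical history are collected at follow-up. A skin cancer that arose on Valchlor would therefore not vanish from the data; what can go unreported is its later elective admission.

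A reader might also take Section 7.1.1 to judge worsening from first Valchlor use. It does not: it dates presence from the earlier date but worsening from the start of the study. Only the anchor for presence is in conflict.

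Finally, there is support for an enrollment baseline. Observation starts at consent (Section 5.3.2), the Table 1 footnote starts safety collection at consent, and Section 5.7.5 defines an on-study event as one on or after the day of enrollment. This does not remove the gap. The admission in question falls after enrollment, Section 7.2 still requires SAEs from Valchlor initiation, and the footnotes to the SAP shells for Tables 18 and 19 count events ongoing at enrollment.

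**Conclusion.** The conflict is real and limited. Section 7.1.2 can exempt an elective or pre-planned admission after enrollment for an unworsened condition that arose on Valchlor before enrollment, and the SAE is lost when hospitalization was its only seriousness criterion. The direction is known: the rule can only lower the SAE count. The size is not known, and no percentage-point bias in the SAE results should be claimed.

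The interval at risk is longer for continuing users, so they have more opportunity to be affected, but the documents do not show that any events were lost in either group. The conclusion assumes that sites apply Section 7.1.2 as written rather than resolving the conflict in favour of Sections 7.1.1 and 7.2.

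**What to change.** Reconcile Section 7.1.2 with Sections 7.1.1 and 7.2:

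- In both exemptions, replace the parenthesis that dates disease from enrollment with the Section 7.1.1 rule: present at treatment initiation or at enrollment, whichever is earlier.
- In the monitoring exemption, review the requirement that the admission was planned before enrollment, so that the item does not carry two different dates.
- Leave worsening as Section 7.1.1 has it, judged from the start of the study. Moving it to first Valchlor use would create a new inconsistency.

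The protocol planned the last visit for Q3 2019 and the SAP is dated November 2019, so collection may already have closed. A change of wording would not then recover admissions that were never reported. In that case, query sites about elective or pre-planned admissions for conditions with onset between first Valchlor use and enrollment, or state the limitation beside SAP Table 19.

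The cost is a small text change, a few more SAE reports or a round of site queries, and possibly a slightly less favourable SAE percentage.

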7.1.3 Relationship to the use of Valchlor

Each AE must be assessed by the investigator as to whether or not there is a reasonable possibility of causal relationship to Valchlor, and reported as either related or unrelated. The determination of the likelihood that Valchlor caused the AE will be provided by an investigator who is a qualified physician.

Related to Valchlor

This category applies to any AE (whether serious or not) that appears to have a reasonable possibility of causal relationship to the use of Valchlor (i.e., a relationship cannot be ruled out). Guidelines to determine whether an event might be considered related include (but are not limited to) the following:

There is temporal relationship between the occurrence of the event and the administration of Valchlor.

The event abated (diminished) or disappeared when treatment with Valchlor was down-titrated, interrupted, or discontinued.

The event recurred when treatment was re-introduced.

Unrelated to Valchlor

This category applies to any AE (whether serious or not) that does not appear to have a reasonable relationship to the use of Valchlor (see above guidelines). Environmental factors such as clinical state and other treatments could equally have caused the event.

